13.1.2.1 Hypotheses

The following hypotheses will be used to evaluate the Primary RV Effectiveness Endpoint 1:

H₀: The RV Pacing Threshold Success Rate \leq 87%

H_A: The RV Pacing Threshold Success Rate $>$ 87%.

13.1.2.2 Sample Size

[REDACTED]

13.1.2.3 Statistical Methods

Multiple RV pacing threshold measurements taken at each of the two visits (MRI Visit and the MRI Visit + 1 Month) will be averaged to determine the average RV pacing threshold at each visit for each subject. The change in average pacing thresholds will then be calculated for each subject and compared to 0.5V to determine success or failure. Subjects that have an increase in average pacing thresholds (pre-MR Scan and at the MRI visit + 1 Month follow-up) \leq 0.5V will be considered a success.

[REDACTED]

All variations of RV leads and lead families will be pooled for this endpoint.

Primary RV Effectiveness Endpoint 1 will be analyzed by per-protocol analysis. The per-protocol analysis will only include subjects who received an MR Scan, and will not include subjects that meet any of the following exclusions:

- Has a medically necessary scan between implant and the MRI + 1 Month Visit
- Fails to meet labeled MRI Conditions of Use

- Experiences a lead-related complication between MRI Visit and the MRI + 1 Month Visit
- Has an incomplete scan based on the ENABLE MRI Study MR Scan Sequences

The per-protocol analysis will consider the subjects without paired RV pacing threshold measurements as having missing data, in addition to any subject that meets an exclusion listed above. To assess the impact missing data could have had on the analysis results, a tipping point analysis will be conducted. The analysis will assign each subject with missing data as either a failure or success. All possible combinations of these patients' data will be evaluated along with the actual observed data to find the point, if any, at which the endpoint has failed.

13.1.3 Primary RV Effectiveness Endpoint 2: Pre-MR scan vs. 1 Month Post-MR Scan RV Sensed Amplitude

Decreases in RV sensed amplitude pre-MR scan and 1 Month post-MR scan will be calculated for subjects. Subjects will be considered a success if the average sensed amplitude at the MRI + 1 Month Visit remains ≥ 5.0 mV and above 50% of the pre-MR scan value. Subjects who have an average pre-scan RV sensed amplitude measurement < 5.0 mV will be excluded from this analysis.

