13.1.3.1 Hypotheses

The following hypotheses will be used to evaluate the Primary RV Effectiveness Endpoint 2:

- H_0 : The RV Sensed Amplitude Success Rate $\leq 85\%$
- H_A : The RV Sensed Amplitude Success Rate $> 85\%$.

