13.1.4.1 Hypotheses

The following hypotheses will be used to evaluate the Primary LV Effectiveness Endpoint 1:

H_0 : The LV Pacing Threshold Success Rate $\leq 87\%$

H_A: The LV Pacing Threshold Success Rate > 87%.

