13.1.5.1 Hypotheses

The following hypotheses will be used to evaluate the Primary LV Effectiveness Endpoint 2:

H₀: The LV Sensed Amplitude Success Rate $\leq 85\%$

H_A: The LV Sensed Amplitude Success Rate $> 85\%$.

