21.4 Adverse Event Classification for FDA Reporting

21.4.1 Observation/Complication

Reported events will be classified, by BSC personnel or trained authorized representatives as a clinical observation or complication; as defined in the Table 21-2.

Table 21-2: Definition of Observation and Complication

Clinical Event	Description
Observation	Adverse event that was transient or reversible and corrected with non-invasive interventions, such as reprogramming or oral medications, or was resolved with no intervention or monitoring
Complication	An adverse event that resulted in: death, serious injury* a, correction using invasive intervention**, or permanent loss of device functions***.

* Per 21 CFR 803.3(bb):

- 1) Serious injury means an injury or illness that:
 - i) Is life-threatening;
 - ii) Results in permanent impairment of a body function or permanent damage to body structure; or
 - iii) Necessitates medical or surgical intervention to preclude permanent impairment of a body function or permanent damage to a body structure.
- 2) Permanent means, for purposes of this subpart, irreversible impairment or damage to a body structure or function, excluding trivial impairment or damage.

** Invasive interventions are those in which treatment necessary to correct the adverse event is delivered by cutting or piercing of the skin or placing an instrument in a body cavity to provide therapy. Examples of invasive interventions (complication) include:

- Surgical revision of a lead
- Electrophysiology study in which an ablation is performed
- Angiogram in which angioplasty or stent placement is performed
- Intravenous medications
- Blood transfusions
- Intubation to provide respiratory support

- Chemical (pharmacologic) Cardioversion with IV sedation (This is a complication due to the IV antiarrhythmic medication used for the cardioversion.)

Invasive procedures that are purely diagnostic in nature should not be considered as a complication. Examples of procedures that are invasive, but not considered to be an intervention (observation), include:

- Blood draw for laboratory analysis
- Cardiac catheterization in which pressures are recorded, but without therapeutic interventions
- Electrophysiology study to map arrhythmias, but without therapeutic intervention
- Transesophageal echo (TEE)
- Electrical (external) Cardioversion with IV sedation (the IV sedation used is for patient comfort and not part of the treatment)

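### All four primary effectiveness analyses drop subjects with a post-scan lead complication, so a tested lead bad enough to be revised leaves the denominator and can push the success rate up.

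*Combined protocol and SAP*

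**What the plan says.** Sections 13.1.2.3, 13.1.3.3, 13.1.4.3 and 13.1.5.3 name a per-protocol analysis for the RV and LV pacing-threshold and sensed-amplitude endpoints. All four lists exclude a subject who "Experiences a lead-related complication between MRI Visit and the MRI + 1 Month Visit". No list says which lead is meant, and none asks whether the scan was the cause.

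Section 21.4.1 decides what counts as a complication. An adverse event corrected by an invasive intervention qualifies, and the first example given is "Surgical revision of a lead". A transient or reversible event that is "corrected with non-invasive interventions, such as reprogramming or oral medications" is only an observation, so that subject stays in.

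The same four sections add a tipping-point analysis. It treats as missing the subjects without paired measurements, "in addition to any subject that meets an exclusion listed above", and tries every assignment of success and failure to them. Section 13.1.1 counts a complication against the safety endpoint if the site reports it as related to the scan and the system and the external committee then attributes it to the scan.

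The goals are 87% for both pacing-threshold endpoints (13.1.2.1, 13.1.4.1) and 85% for both sensed-amplitude endpoints (13.1.3.1, 13.1.5.1). The test is a one-sided exact binomial test (Protocol Synopsis) at 5% per endpoint (13.4.2).

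**The concern.** The exclusion is defined by something that happens after the scan and that the scan could cause. It therefore selects on the outcome. An RV threshold rise just over 0.5 V that needs no invasive correction stays in the denominator as a failure. An RV lead that deteriorates until it is revised leaves the denominator.

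This runs against section 13.2.3, which reads an endpoint failure as a possible scan effect on the corresponding lead. On that reading, the most severe outcomes are the ones the endpoint should keep.

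The direction is not automatic. Some excluded subjects would have been successes, for example on the RV endpoints after an RA lead revision. Bias is upward only if failures are over-represented among those removed. That is plausible for complications of the tested lead and less so for complications of another lead.

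At stake is whether a pass against a fixed goal in a one-arm study describes all scanned subjects or only those whose leads did well enough to remain.

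**Working it through.** The plan has no figure to reproduce: the sample-size sections and the synopsis columns for expected rate, N and attrition are redacted. The sample sizes and removal rates below are assumptions.

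**Inputs**
- Goals p0 = 0.87 and 0.85; one-sided exact binomial test; alpha 0.05.
- n = 100, 150, 250 and 350 scanned subjects (assumed).
- r = share of scanned subjects removed; q = share of those removed who are true failures (both assumed).
- Two values of r can be loosely anchored in the Introduction, as upper 95% bounds on zero events. For 0 of 829 cases, 1 − 0.05^(1/829) = 0.36%. For 0 of 488 patients with a change needing system revision or reprogramming, 1 − 0.05^(1/488) = 0.61%. Both describe scanned series, whereas the exclusion covers any cause, so the true r could be higher.

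**Direction of bias.** If the true success rate in all scanned subjects is p0, the rate in those retained is

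(p0 − r(1 − q)) / (1 − r).

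This exceeds p0 exactly when q > 1 − p0. The bias is upward once more than 13% (87% goal) or 15% (85% goal) of those removed are failures.

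**Type I error of one endpoint, true success exactly at the goal (%).** The number removed is Bin(n, r); the rest are tested at p0.

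| Goal | r | q | n=100 | 150 | 250 | 350 |
|---|---|---|---|---|---|---|
| 87% | 0 | – | 4.31 | 3.84 | 4.06 | 3.63 |
| 87% | 0.36% | 1 | 5.30 | 5.00 | 5.70 | 5.48 |
| 87% | 0.36% | 0.5 | 4.77 | 4.38 | 4.82 | 4.48 |
| 87% | 0.61% | 1 | 6.04 | 5.96 | 7.09 | 7.17 |
| 87% | 0.61% | 0.5 | 5.07 | 4.80 | 5.38 | 5.15 |
| 85% | 0 | – | 2.75 | 4.93 | 3.42 | 4.64 |
| 85% | 0.36% | 1 | 3.41 | 5.14 | 4.76 | 6.03 |
| 85% | 0.36% | 0.5 | 3.06 | 4.55 | 4.04 | 5.01 |
| 85% | 0.61% | 1 | 3.94 | 5.53 | 5.93 | 7.12 |
| 85% | 0.61% | 0.5 | 3.30 | 4.49 | 4.53 | 5.22 |

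Purely hypothetical rates of 1.3% and 2.6% (10% and 20% of the 13% failures at the 87% goal) give about 8-14% and 13-33% if all removed are failures, and 5.7-7.3% and 6.6-11.5% if half are.

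**Near the boundary.** Returning one failure can reverse a pass:
- 87% goal: 93/100 (p = 0.043) becomes 93/101 (p = 0.079).
- 85% goal: 135/150 (p = 0.049) becomes 135/151 (p = 0.076).

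For just-passing results at n = 100, 150, 200, 250, 300 and 350, one returned failure is enough in most cases and two in the rest.

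**Well clear of the goal.** At about 95% observed success (95/100, 142/150, 238/250, 332/350), reversal needs 3, 5, 13 and 20 returned failures at 87%, or 5, 9, 19 and 27 at 85%.

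**Is the safety endpoint a substitute?** Its goal is 90% (13.1.1.1), tested at 2.5% (13.4.2). Using an exact binomial test to approximate the planned Kaplan-Meier analysis, it still passes with up to 4, 7, 15 and 23 events at n = 100, 150, 250 and 350.

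**The case against.** The strongest reply is that the plan already contains the answer. The tipping-point analysis covers every assignment, including the one in which every excluded subject failed, so the worst case will be known. Complications attributed to the scan have their own primary endpoint, tested at a stricter level, and under the Intersection-Union Test it must also pass. Keeping complications in safety and measurements in effectiveness is a coherent division.

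Few subjects may leave: the Introduction reports no lead replacements and no system revisions in two scanned series. With the anchored rates and half of those removed failing, type I error is close to nominal; at the 85% goal with n = 150 it even falls slightly, from 4.93% to 4.49% at r = 0.61%, because the test is discrete. Parts of 13.1.2.3, 13.1.4.3 and 13.1.5.3 are redacted, so a decision rule may exist out of sight. De novo subjects are scanned 6-9 weeks after implant, so scoring every revision as a failure would charge some implant problems to the scan.

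Much of this stands as a limit on size. It does not repair the primary test. The visible text attaches no consequence to the tipping-point result, and that analysis also allows a revised lead to be scored as a success. The safety endpoint sees only events that the site first reports as related, and it can pass with several of them. The objection about implant-related revisions is a real cost, and the supportive per-protocol analysis would show how large it is.

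**Conclusion.** The concern holds. The exclusion depends on a post-scan outcome, appears in all four primary effectiveness analyses, and is limited neither by lead nor by cause. Combined with the definitions in 21.4.1, it can remove the worst outcomes of the tested lead while milder ones count as failures.

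The structure is clear from the text; the size is not. With removal rates loosely anchored in the Introduction, one endpoint's type I error reaches at most about 7%, and only if every removed subject is a failure. Larger inflation needs the hypothetical rates. These figures assume a true success rate exactly at the goal. Under the plan's Intersection-Union Test, the error of the overall claim is no larger than that of a single endpoint. A result near the goal could turn on one or two subjects; a result near 95% would probably not change. This should be fixed because the correction is cheap, with medium confidence that it matters in practice.

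**What to change.** In 13.1.2.3, 13.1.3.3, 13.1.4.3 and 13.1.5.3:

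1. Remove the lead-related-complication exclusion from the primary analysis.
2. Analyse every such subject who has valid paired measurements of the same tested lead on those measurements, including subjects whose complication involved only another lead.
3. Score an endpoint as a failure only when, between the scan and the MRI + 1 Month Visit, a complication of the tested lead caused it to be revised, replaced or taken out of use, or made it unmeasurable for that endpoint. Such a subject then does not simply become missing.
4. Keep the present per-protocol set and the tipping-point analysis as supportive.

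No new measurements are needed, since all implanted leads are already evaluated at the MRI + 1 Month Visit (12.8.1). Someone must decide that the tested lead's own complication was the reason; the events committee's listed remit (23.1) does not clearly cover this, although the sponsor may send it further events. The change alters four primary analysis sets and needs an amended SAP approved before the analysis (13.5.5); section 11.1.1 shows that some subjects may already have been scanned. Some revisions unrelated to the scan will count as failures, so the reported rate may be lower.

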13.1.3.1 Hypotheses

The following hypotheses will be used to evaluate the Primary RV Effectiveness Endpoint 2:

- H_0 : The RV Sensed Amplitude Success Rate $\leq 85\%$
- H_A : The RV Sensed Amplitude Success Rate $> 85\%$.

13.1.3.2 Sample Size

[REDACTED]

13.1.3.3 Statistical Methods

Multiple RV sensed amplitude measurements taken at each of the two visits (MRI Visit and the MRI + 1 Month Visit) will be averaged to determine the average RV sensed amplitude at each visit for each subject. The percent of subjects meeting the success criteria will be calculated.

All variations of RV leads and lead families will be pooled for this endpoint.

Primary RV Effectiveness Endpoint 2 will be analyzed by per-protocol analysis. The per-protocol analysis will only include subjects who received an MR Scan, and will not include subjects that meet any of the following exclusions:

- Has a medically necessary scan between implant and the MRI + 1 Month Visit
- Fails to meet labeled MRI Conditions of Use
- Experiences a lead-related complication between MRI Visit and the MRI + 1 Month Visit
- Has an incomplete scan based on the ENABLE MRI Study MR Scan Sequences
- Average RV sensed amplitude <5mV pre-MR scan

The per-protocol analysis will consider the subjects without paired RV sensed amplitude measurements as having missing data, in addition to any subject that meets an exclusion listed above. To assess the impact missing data could have had on the analysis results, a tipping point analysis will be conducted. The analysis will assign each subject with missing data as either a failure or success. All possible combinations of these patients' data will be evaluated along with the actual observed data to find the point, if any, at which the endpoint is failed.

13.1.4 Primary LV Effectiveness Endpoint 1: Pre MR Scan- vs. 1 Month Post-MR Scan LV Pacing Threshold at 0.5 ms

Increases in average LV pacing threshold (at 0.5 ms) pre- MR scan and 1 Month post-MR scan will be calculated for subjects. Subjects that have an increase in pacing thresholds measurements $\leq 1.0V$ (at 0.5 ms) from pre-MR Scan at MRI Visit to MRI + 1 Month Visit will be considered a success.

13.1.4.1 Hypotheses

The following hypotheses will be used to evaluate the Primary LV Effectiveness Endpoint 1:

H_0 : The LV Pacing Threshold Success Rate $\leq 87\%$

H_A: The LV Pacing Threshold Success Rate > 87%.

13.1.4.2 Sample Size

[REDACTED]

[REDACTED]

[REDACTED]

[REDACTED]

[REDACTED]

[REDACTED]

[REDACTED]

[REDACTED]

[REDACTED]

[REDACTED]

[REDACTED]

13.1.4.3 Statistical Methods

Multiple LV pacing threshold measurements taken at each of the two visits (MRI Visit and the MRI + 1 Month Visit) will be averaged to determine the average LV pacing threshold at each visit for each subject. The change in average pacing thresholds will then be calculated for each subject and compared to 1.0V to determine success or failure, and the percent of subjects meeting the success criteria will be calculated. [REDACTED]

[REDACTED]

Primary LV Effectiveness Endpoint 1 will be analyzed by per-protocol analysis. The per-protocol analysis will only include subjects who received an MR Scan, and will not include subjects that meet any of the following exclusions:

- Has a medically necessary scan between implant and the MRI + 1 Month Visit
- Fails to meet labeled MRI Conditions of Use
- Experiences a lead-related complication between MRI Visit and the MRI + 1 Month Visit
- Has an incomplete scan based on the ENABLE MRI Study MR Scan Sequences

The per-protocol analysis will consider the subjects without paired LV pacing threshold measurements as having missing data, in addition to any subject that meets an exclusion

listed above. To assess the impact missing data could have on the analysis results, a tipping point analysis will be conducted. The analysis will assign each subject with missing data as either a failure or success. All possible combinations of these patients' data will be evaluated along with the actual observed data to find the point, if any, at which the endpoint has failed.

13.1.5 Primary LV Effectiveness Endpoint 2: Pre-MR scan vs. 1 Month Post-MR Scan LV Sensed Amplitude

Decreases in average LV sensed amplitude pre-MR scan and 1 Month post-MR scan will be calculated for subjects. Subjects will be considered a success if the average sensed amplitude at the MRI + 1 Month Visit remains ≥ 5.0 mV and above 50% of the average pre-MR Scan value. Subjects who have an average pre-scan LV sensed amplitude measurement < 5.0 mV will be excluded from this analysis.

13.1.5.1 Hypotheses

The following hypotheses will be used to evaluate the Primary LV Effectiveness Endpoint 2:

H₀: The LV Sensed Amplitude Success Rate $\leq 85\%$

H_A: The LV Sensed Amplitude Success Rate $> 85\%$.

13.1.5.2 Sample Size

[Redacted]

[Redacted]

[Redacted]

[Redacted]

[Redacted]

[Redacted]

[Redacted]

13.1.5.3 Statistical Methods

Multiple LV sensed amplitude measurements taken at each of the two visits (MRI Visit and the MRI + 1 Month Visit) will be averaged to determine the average LV sensed amplitude at each visit for each subject. The percent of subjects meeting the success criteria will be calculated. [Redacted]

Primary LV Effectiveness Endpoint 2 will be analyzed by per-protocol analysis. The per-protocol analysis will only include subjects who received an MR Scan, and will not include subjects that meet any of the following exclusions:

- Has a medically necessary scan between implant and the MRI + 1 Month Visit
- Fails to meet labeled MRI Conditions of Use
- Experiences a lead-related complication between MRI Visit and the MRI + 1 Month Visit
- Has an incomplete scan based on the ENABLE MRI Study MR Scan Sequences
- Average LV sensed amplitude <5mV pre-MR scan

The per-protocol analysis will consider the subjects without paired LV sensed amplitude measurements as having missing data, in addition to any subject that meets an exclusion listed above. To assess the impact missing data could have had on the analysis results, a tipping point analysis will be conducted. The analysis will assign each subject with missing data as either a failure or success. All possible combinations of these patients' data will be evaluated along with the actual observed data to find the point, if any, at which the endpoint is failed.

13.2 Ancillary Assessments

The ancillary endpoints are not formal endpoints and are not statistically powered.

13.2.1 Assessment of RV and LV Impedances

The changes in RV and LV impedances pre-MR scan versus 1 Month post-MR scan (MRI Visit and MRI + 1 Month Visit) will be presented in the study report. There are no success criteria for impedances, so a failure rate will not be presented.

13.2.2 Assessment of RA lead measurements

The changes in RA lead measurements including pacing thresholds, sensed amplitudes and impedances, between pre- and 1 Month post-MR scan measurements will be presented in the study report. Also a summary by lead family, INGEVITY MRI and FINELINE II, will be presented. There are no success criteria for RA lead measurements, so a failure rate will not be presented.

13.2.3 Assessment on MR Scan Effect on Lead Measurements

If a subject fails any of the effectiveness endpoints, it may indicate a potential MR scan effect on the corresponding lead for that endpoint. However if the same subject fails both the pacing threshold and sensed amplitude effectiveness endpoints, this would represent stronger evidence of MR Scan effect on the corresponding lead. Summaries of the subjects failing

both the pacing threshold and sensed amplitude effectiveness endpoints for each chamber will be included in the study report.

13.2.4 Assessment of VT/VF

In Phase I, VT and VF episodes from the following three sources will be collected and analyzed:

- Spontaneous VT/VF episodes that required therapy
- VT/VF episodes from “for-cause” VF induction
- VF Induction Sub-study VT and VF episodes

The VT/VF episodes will be evaluated by an ECG Core Lab. The performance objective is to demonstrate the continued ability of the ImageReady MR Conditional Defibrillation System to sense and detect VF post-MR scan (Phase I). Any instances of a detection delay of ≥ 5 seconds above the detection time expected, based on the VF rate and programming, will be further evaluated and the analysis will be provided.

In addition, Boston Scientific plans to collect available spontaneous VT/VF episodes post MR scan from Phase I and II subjects over a 3-year follow-up period. The VT/VF episodes will be evaluated by an ECG core lab. A summary of the results from the ECG core lab will be included in the study report.

13.2.5 Assessment of Effect of Medically Necessary MR Scans

Boston Scientific proposes to collect available data on medically necessary MR scans (MNS) from Phase I and II subjects over a 3-year follow-up period. A summary of changes in lead measurements pre- to post- MNS and any MNS related complications will be presented.

To assess the additive effect of multiple MR scans, the same summaries will be done for subjects with multiple MR scans.

